### **Patients and methods:**

Patients undergoing major abdominal surgery will be included in the study. A major surgical procedure in the abdomen will be considered all procedures that require a surgical approach by laparotomy, which include resections of parts of the organs of the digestive system. Organic dysfunction will be considered laboratory or clinical signs of decreased renal function measured by diuresis with laboratory increase in serum nitrogen metabolites (increase by  $\geq 30\%$  of normal values), and decrease in liver function measured by increase in liver enzymes (increase by  $\geq 30\%$  of reference values), by a decrease in serum cholinesterase levels ( $\leq 20\%$  of normal), an increase in bilirubin by 30% of normal, or a decrease in synthetic liver function as measured by prolongation of PV to  $\leq 60\%$  of INR. A systemic inflammatory response will involve the perioperative presence of two or more of the following factors: body temperature  $> 38$  oC or  $< 36$  oC, leukocytes  $> 12,000$  or  $< 4,000$  mm^3, pCO2  $< 4.3$  kPa, and pulse  $> 90$  / min. In addition, a perioperative increase in CRP, PCT, and lactate above reference values,

as well as a decrease in serum cholinesterase levels, will be considered a systemic inflammatory response. Patients who have a known allergic reaction to tramadol, and patients who have received tramadol for the past 7 days, patients younger than 18 years, BMI <18 kg / m^2> 40 kg / m^2, and patients who do not sign the informed consent will be excluded from the study. Also excluded from the study will be patients who have had laparoscopic surgery, as well as those on chronic therapy with cimetidine, paroxetine, pimozide, metoclopramide, amiodarone, olanzapine, chlorpromazine, fluphenazine, haloperidol, thioridazine, risoridazine, risoridazine drugs inhibit the activity of CYP2D6 enzyme important in tramadol metabolism.

After signed informed consent, all patients included in the study will have a blood sample taken for analysis of the CYP2D6 polymorphism, and ultrafast and slow metabolizers will be excluded from further analysis. A commercial set of "High Pure PCR Template Preparation Kit" according to the manufacturer's instructions (Roche Life Science) will be used to isolate the genomic DNA of the subjects. DNA isolation will be performed from whole blood samples with the anticoagulant EDTA. The protocol consists of lysis of blood cells using lysis buffer, degradation of protein by proteinase K, separation of DNA molecules from the mixture, and purification of DNA using glass mesh columns in a series of washing and centrifugation steps. Measurement of the isolated DNA concentration will be performed using a UV / VIS nanospectrophotometer. DNA samples will be stored at -20 oC until the testing procedure. To determine the allelic variants CYP2D6 \* 3 (rs35742686), CYP2D6 \* 4 (rs3892097) and CYP2D6 \* 5 (whole gene deletion), the commercial set LightMix Kit CYP2D6 \* 3 \* 4 \* 5 / \* 5 will be used according to the manufacturer's instructions (TibMolbiol). The method is real-time PCR (real-time polymerase chain reaction). The test is based on the use of a certain type of fluorescently labeled hybridization assays, the so-called "SimpleProbe" that specifically binds to a sequence that includes a targeted change in DNA. Commercial sets "CYP2D6 TaqMan Copy Number Assay" and "TaqMan Copy Number Reference Assay" according to the manufacturer's instructions (Applied Biosystems) will be used to determine duplication / amplification and the number of copies of the CYP2D6 gene (CYP2D6 \* 1xN). The method is real-time PCR, and the assay is based on the use of fluorescently labeled specific TaqMan probes that bind to the target gene sequence and reference TaqMan probes that bind to a reference sequence that is known to be present in the diploid genome. Relative quantification of the number of copies of the CYP2D6 gene will be possible by analyzing the results using CopyCaller (Applied Biosystems).

After induction under general anaesthesia, in addition to standard laboratory findings, plasma concentrations of albumin, cholinesterase, gamma-glutamyltransferase, bilirubin, C-reactive protein, procalcitonin will be measured, and pH, pO2, pCO2 and lactate values will be determined from an arterial blood sample. During the procedure, patients will be anesthetized by the method of general balanced inhalation anaesthesia with sevoflurane. Postoperatively, vital parameters, such as temperature, pressure, pulse and diuresis, will be continuously monitored in the ICU, and postoperative values of arterial blood gases, lactate and routine laboratory findings - complete blood count - will be determined. In the ICU patients will receive a total of 500 mg of tramadol intravenously divided into 5 doses during the first 24 hours of admission to ICU.

Plasma concentrations of tramadol, O-demethyltramadol and N-demethyltramadol will be measured 1, 2 and 4 hours after the first dose, and immediately before the 2nd, 3rd and 5th doses. In total, therefore, there will be 6 measurements within 24 hours. Determination of the concentration of tramadol and ODT and NDT metabolites from patient

plasma samples will be performed by high performance liquid chromatography (HPLC) on a Shimadzu Nexera XR (Shimadzu Corporation, Kyoto, Japan) on a reverse phase chromatographic system with fluorescence detection (excitation wavelength 200 a emission 301 nm). Separation will be performed on an Agilent Zorbax SB-C8 column, 3.5  $\mu$ m, 4.6x150 mm (Agilent Technologies, Santa Clara, CA, USA) using a mobile phase consisting of methanol and 1.5 mM H3PO4 in a ratio of 19:81), pH 2.5.

The analgesic effect of tramadol will be measured in patients who are conscious on the NRS scale (0 - no pain, 10 - most severe pain) 30 minutes before and 30 minutes after tramadol administration. An NRS value of 3 or less will be considered adequate analgesia, and in case of inadequate analgesia, an additional analgesic will be used - morphine 2 mg. In patients with impaired consciousness, the analgesic effect of tramadol will be examined by the Behavioral Pain Scale (BPS) (3 - no pain, 12 - most severe pain) and the Critical Care Pain Observation Tool (CPOT). A BPS value of 5 or less will be considered adequate analgesia, as well as CPOT values less than 2. Consumption of additional analgesic will be recorded regularly. Nausea, vomiting, and newly developed respiratory depression will be reported within 24 hours. In all patients, they will record the total time of hospitalization in ZIM, hospitalization and the patient's outcome - death or survival until discharge from the hospital.

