## Background

Tramadol is a commonly used opioid analgesic for the treatment of moderate to severe acute and chronic pain. It is metabolized in the liver by O- and N-demethylation (phase I) and conjugation (phase II). O-demethylation of tramadol to the active metabolite O-demethyltramadol (ODT) is catalyzed by cytochrome CYP2D6, and N-demethylation to N-demethyltramadol (NDT) occurs via CYP2B6 and CYP3A4. The ODT metabolite of tramadol is an active metabolite that has 200-fold higher affinity for opioid receptors than tramadol itself and is thought to be responsible for the bulk of the analgesic effect of tramadol. CYP2D6 is a non-inducible enzyme, and its gene shows marked polymorphism due to which there are large individual and population differences in metabolism, analgesic action, and side effects of tramadol. Individuals carrying two inactive copies of CYP2D6 are poor metabolizers (PM) of tramadol compared to those carrying two copies of the extensive wild allele (EM). Individuals carrying one or more copies of inactive alleles or alleles of reduced CYP2D6 activity are intermediate metabolizers (IM), and those carrying more than two copies of wild alleles for CYP2D6 are ultrarapid metabolizers (UM). In addition to pharmacogenetics, the functional status of the liver and kidneys plays an important role in the pharmacokinetics of tramadol. Tramadol and the ODT metabolite are excreted by the kidneys, therefore renal failure, which is common in intensive care units (ICU), leads to the accumulation of tramadol and the ODT metabolite in the blood. More than 80% of tramadol is metabolized in the liver. There are known to be significant differences in the pharmacokinetics of tramadol between healthy subjects and patients with hepatic failure. In patients with hepatic failure, tramadol plasma concentrations are higher and the elimination half-life is longer. These changes are primarily due to decreased hepatic elimination. Patients in ICU often have mildly reduced liver function as part of multiorgan failure due to sepsis or Systemic Inflammatory Response Syndrome (SIRS), while major abdominal surgery and anaesthesia reduce liver perfusion and contribute to hypoxic liver damage. Drug distribution changes as a result of decreased protein production and changes in extracellular volume, and the activity and metabolic capacity of liver enzymes decreases resulting in increased concentration and decreased plasma elimination of drugs, which is often very difficult to predict. The CYP2D6 genotype-phenotype has been shown to be relatively effective in clinical practice, but it should be noted that a number of genotype-phenotype discrepancies have been documented, therefore the absorption, distribution, metabolism and excretion of tramadol cannot be determined by a single protein genotype. The expression and activity of CYP2D6 is regulated by a number of physiological, pathological and environmental factors. CYP2D6 expression is susceptible to changes in infection states or systemic inflammatory response associated with elevated cytokine values. Expression of CYP2D mRNA and protein is reduced by proinflammatory cytokines in the liver of mice and rats, while administration of anti-inflammatory cytokines such as IL-10 reduces CYP3A activity. This decrease was not observed for CYP2D. At low CYP2D6 activity or when O-demethylation of tramadol is reduced, tramadol is primarily metabolized by N-demethylation. A study in cancer patients known to have a chronic inflammatory condition accompanied by elevated values of proinflammatory mediators showed that elevated IL-6 values correlated with N-demethylation of tramadol and patient tolerance to the analgesic effect of tramadol. Surgical stress, anaesthesia, starvation, postoperative pain, emergency surgery, and surgery for malignant diseases contribute to the development of a systemic inflammatory response. Hypothermia or hyperthermia, leucocytosis or leukopenia, tachycardia and tachypnoea, are clinical components of SIRS which is often difficult to distinguish clinically from acute inflammation, but in both conditions

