### **Objectives**

1. measure the plasma concentrations of tramadol, O-demethyltramadol and N-demethyltramadol in a patient admitted to the intensive care unit (ICU) after major abdominal surgery;
2. examine differences in tramadol, ODT and NDT concentrations with respect to CYP2D6 gene polymorphism;
3. examine the effect of systemic inflammation on the concentrations of tramadol, ODT and NDT in the early postoperative period;
4. examine the analgesic effect of tramadol with respect to systemic inflammation and organic dysfunction.

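### Liver resections are not excluded and a fall in cholinesterase counts as inflammation, so Objective 3 can show an inflammation effect that is partly the operation.

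*Combined protocol and SAP*

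**What the plan says.** All references are to the combined protocol and SAP.

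- **Eligibility (Patients and methods).** Eligible operations are laparotomies that include "resections of parts of the organs of the digestive system". The only exclusion by type of operation is for laparoscopy: "Also excluded from the study will be patients who have had laparoscopic surgery". Liver resection and liver disease are neither named nor excluded.
- **Organ dysfunction (Patients and methods).** Reduced liver function may be shown, among other signs, "by a decrease in serum cholinesterase levels", with a cut-off of 20% of normal or less.
- **Inflammation (Patients and methods).** Besides the usual clinical criteria, a perioperative rise in CRP, PCT and lactate, "as well as a decrease in serum cholinesterase levels, will be considered a systemic inflammatory response". No cholinesterase threshold is given here.
- **Sampling (Patients and methods).** Cholinesterase is listed in the sample taken after induction. The postoperative list names blood gases, lactate and routine laboratory findings (blood count), but not cholinesterase.
- **Pharmacology (Background).** "More than 80% of tramadol is metabolized in the liver", and "In patients with hepatic failure, tramadol plasma concentrations are higher and the elimination half-life is longer".
- **Objective 3 (Objectives).** "examine the effect of systemic inflammation on the concentrations of tramadol, ODT and NDT in the early postoperative period".
- **Analysis (Statistical analysis plan).** Two-group and multi-group tests, correlations and repeated-measures tests. There is no covariate, stratum, multivariable model or sensitivity analysis, and type of operation is not mentioned.

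**The concern.** Inflammation status is observed, not randomised, so anything that moves both the label and the concentration confounds Objective 3. Liver resection may do both. It removes tissue that metabolises tramadol, which should raise the parent drug. It may also lower cholinesterase, which the protocol itself uses as a sign of liver function and also counts as inflammation. That tissue loss lowers cholinesterase is an inference from this use; the documents do not say it.

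If the inflamed group then holds more liver resections, an unadjusted test can find higher tramadol concentrations in that group even when inflammation has no effect. The reader of the results could not tell the two explanations apart.

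**Working it through.** The documents give no sample size, effect size, SD or share of liver resections, so there is no planned figure to reproduce. The steps below show what the mechanism would do under stated assumptions, with a true inflammation effect of zero.

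**1. Exposure after resection.** Take a hepatic share of 0.8 (Background, which says more than 80%) and assume that clearance falls in proportion to the fraction f of liver removed.

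Exposure ratio = 1 / (1 − 0.8f)

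- f = 0.25: 1 / 0.80 = 1.25
- f = 0.50: 1 / 0.60 = 1.67

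**2. Spurious group ratio.** Let s be the share of liver resections among inflamed patients minus the share among the others. The spurious geometric mean ratio is (exposure ratio)^s.

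- Low end: 1.25^0.10 = 1.02
- High end: 1.67^0.30 = 1.17

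**3. What share of liver resections gives such an imbalance?** Assume that every liver resection is labelled inflamed, as is a fraction q of the other patients. With p the share of liver resections in the cohort, s = p / (p + q(1 − p)).

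- q = 0.4: s = 0.10 needs p of about 4%, and s = 0.30 needs p of about 15%.
- q = 0.8: s = 0.30 needs p of about 26%.
- p = 5%: s = 0.05 / (0.05 + 0.76) = 0.062 for q = 0.8, and 0.05 / (0.05 + 0.38) = 0.116 for q = 0.4. The spurious ratio then runs from 1.25^0.062 = 1.01 to 1.67^0.116 = 1.06.

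**4. Early samples.** Step 1 gives a steady-state (or total) exposure ratio. Three of the six samples fall 1, 2 and 4 hours after the first dose. In a one-compartment model the ratio at time t is exp(0.8f × k × t), with k = ln 2 / half-life. The half-life of 4 to 8 hours is an assumption.

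| Time | f = 0.25, half-life 8 h | f = 0.50, half-life 4 h |
|---|---|---|
| 1 h | 1.02 | 1.07 |
| 2 h | 1.04 | 1.15 |
| 4 h | 1.07 | 1.32 |

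At 4 h the spurious group ratio is therefore 1.07^0.10 = 1.01 to 1.32^0.30 = 1.09, below the range in step 2. Later pre-dose samples can reach or exceed the step 2 range.

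**5. Effect on the planned test.** This is an illustrative simulation: Mann-Whitney, two-sided 0.05, N = 100, 1000 runs per cell, q = 0.4, all liver resections labelled inflamed. Liver resection shifts concentration by 0.5 to 1.0 SD. The spurious difference is shift × s.

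| Liver resections | s | Spurious difference (SD) | False-positive rate |
|---|---|---|---|
| 5% | 0.116 | 0.058 to 0.116 | 5 to 8% |
| 10% | 0.217 | 0.109 to 0.217 | 8 to 16% |
| 20% | 0.385 | 0.192 to 0.385 | 15 to 38% |
| 30% | 0.517 | 0.259 to 0.517 | 20 to 64% |

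Across N = 60, 100 and 200, leaving out liver resections returned the rate to about 4 to 6.5%. At N = 100, when cholinesterase did not drive the label, the rate was about 4.5 to 6% with all patients kept.

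**The case against.** **The mechanism may have no measurement behind it.** The only cholinesterase sample that the protocol lists precedes the resection, and removed tissue cannot lower a value taken before it was removed. This stands as a condition. The word perioperative in the inflammation definition implies a later value, but the schedule does not show one.

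**The label may not depend on cholinesterase alone.** The definition does not say whether one of CRP, PCT, lactate and cholinesterase suffices or all must change. If all must, cholinesterase by itself labels nobody. This also stands as a condition. A reader might infer that liver resections are bound to be classed as inflamed; the text does not go that far.

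**Low cholinesterase is a reasoned choice.** The Background presents it as an early marker of systemic inflammation. That supports measuring it, but it does not show that a fall after loss of liver tissue reflects inflammation.

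**Liver resection is only part of the cause.** The Background says that major abdominal surgery and anaesthesia reduce liver perfusion, so the double use of cholinesterase can blur the contrast after other operations too. This is right, and dropping liver resections alone would not cure it.

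**Objective 4.** A reader might extend the concern to the organ dysfunction contrast. The documents do not support that. Objective 4 concerns analgesic effect, and reduced liver function after resection is genuine organ dysfunction, which is the exposure of interest there.

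**Adjustment.** A reader might also infer that adjusting for any liver test is futile because it forms part of the inflammation label. That is true only of cholinesterase. Bilirubin, gamma-glutamyltransferase and the other liver tests are not in that label.

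**Conclusion.** The concern holds as a possible bias in Objective 3. The text supports four links: liver resections are not excluded, cholinesterase serves two definitions, tramadol is mainly metabolised in the liver, and no planned analysis separates the operations. The bias arises if a postoperative cholinesterase value is used and if that marker alone can set the label. The sponsor needs to settle both.

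Its size cannot be fixed from the documents. Under the assumed loss of 25 to 50% of the liver and an imbalance of 10 to 30 percentage points, the spurious ratio is about 1.02 to 1.17 for steady-state exposure. It is smaller at 1 to 4 hours, and about 1.01 to 1.06 if liver resections are 5% of the cohort. The figures concern the parent drug only; the metabolites were not modelled.

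It would be tempting to add that the bias favours the study hypothesis. No hypothesis is stated: Objective 3 only asks what the effect is, and the Background at most suggests a direction.

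**What to change.** 1. Record liver resection (yes/no) from the operation note.
2. For Objective 3, report the inflammation contrast with and without liver resections.
3. Repeat that contrast with inflammation defined without cholinesterase, since the overlap is not confined to liver surgery.
4. State when cholinesterase is sampled, which value enters the definition, and whether cholinesterase alone can set the inflammation label.
5. Keep liver resections in the main Objective 4 analysis.

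The cost is one recorded item, a few lines in the SAP and some additional analysis. The restricted contrast will contain slightly fewer patients.

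### Only chronic users of the listed CYP2D6 inhibitors are excluded; use around surgery or in the ICU is neither recorded nor analysed, and could bias the Objective 3 contrast in either direction if it differs by inflammation status

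*Combined protocol and SAP*

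**What the plan says.** Under Patients and methods, the exclusion covers patients "as well as those on chronic therapy with cimetidine, paroxetine, pimozide, metoclopramide, amiodarone" and further named drugs, haloperidol among them. The reason given is that these "drugs inhibit the activity of CYP2D6 enzyme important in tramadol metabolism". The criterion has no time window, whereas prior tramadol has one: the plan also excludes "patients who have received tramadol for the past 7 days".

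The Background links this enzyme to the outcomes:
- "O-demethylation of tramadol to the active metabolite O-demethyltramadol (ODT) is catalyzed by cytochrome CYP2D6".
- "At low CYP2D6 activity or when O-demethylation of tramadol is reduced, tramadol is primarily metabolized by N-demethylation".
- "CYP2D6 expression is susceptible to changes in infection states or systemic inflammatory response associated with elevated cytokine values".
- "N-demethylation to N-demethyltramadol (NDT) occurs via CYP2B6 and CYP3A4".

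Six plasma samples are taken within 24 hours. Over the same period, "Nausea, vomiting, and newly developed respiratory depression will be reported within 24 hours". The only co-medication that the plan says will be recorded is the additional analgesic. The Statistical analysis plan lists group tests, correlations and repeated-measures tests. It has no covariate, stratification or sensitivity analysis for other drugs.

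**The concern.** The stated reason for the exclusion is enzyme inhibition, which matters while tramadol is being metabolised. How long the patient has been taking the inhibitor is a different matter. A listed drug first given during anaesthesia or in the ICU falls outside the criterion but could act inside the sampling window.

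Objective 3 asks whether systemic inflammation changes tramadol, ODT and NDT. By the plan's own account, inflammation may alter CYP2D6, and low CYP2D6 activity moves metabolism from O- to N-demethylation. An inhibitor could produce that same pattern. The design is observational and the group tests are unadjusted. If inhibitor use is not recorded, no later analysis can separate the two explanations.

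**Working it through.** **1. Does another part of the plan close the gap?** No.
- The chronic-use exclusion does not reach new or short-term use.
- Removing slow and ultrafast metabolizers works on genotype, which cannot show activity lost to a drug.
- Recording the additional analgesic does not capture the listed drugs.
- Recording nausea and vomiting does not capture what is given for them.

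**2. Is there a figure in the plan to reproduce?** No. The documents give no sample size, effect size, standard deviation or usage rate. Everything below is an illustration under assumptions.

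**3. Apparent ODT ratio with no true inflammation effect.** Let r be the proportional fall in ODT in an exposed patient, and p1 and p0 the shares exposed in the inflamed and other groups. Then

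ratio (inflamed / other) = (1 − r·p1) / (1 − r·p0).

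| r | p1 | p0 | Ratio | Apparent difference in inflamed patients |
|---|---|---|---|---|
| 0.2 | 0.2 | 0.1 | 0.96/0.98 = 0.980 | 2.0% lower |
| 0.4 | 0.3 | 0.1 | 0.88/0.96 = 0.917 | 8.3% lower |
| 0.6 | 0.4 | 0.1 | 0.76/0.94 = 0.809 | 19.1% lower |
| any | equal | equal | 1.00 | none |
| 0.2 | 0.1 | 0.2 | 0.98/0.96 = 1.021 | 2.1% higher |
| 0.6 | 0.1 | 0.4 | 0.94/0.76 = 1.237 | 23.7% higher |

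The sign therefore depends wholly on which group is exposed more.

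**4. Effect on a nominal two-sided 5% test.** Assume a coefficient of variation (CV) of 0.5 and 50 patients per group. The variance in a group with exposed share p is CV²·[p(1 − r)² + (1 − p)] + p(1 − p)r². For r = 0.5 and exposure of 30% v 10%:
- Difference in means: 0.95 − 0.85 = 0.10.
- Variances: 0.24625 and 0.25375, which sum to 0.50.
- Standard error: √(0.50/50) = 0.10, so the shift is 1.0 standard error.
- Rejection rate: Φ(1.0 − 1.96) + Φ(−1.0 − 1.96) ≈ 17%.

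Other cases with 50 per group: about 7% for r = 0.2 and 30% v 10%; about 54% for r = 0.5 and 50% v 10%; 5% for r = 0.5 and 20% v 20%.

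**5. Cost of equal use.** For r = 0.5 and 20% exposed in both groups, the variance is 0.25 × 0.85 + 0.04 = 0.2525 and the mean is 0.90. The CV becomes √0.2525 / 0.90 = 0.56 instead of 0.50. That is a loss of precision without bias in the contrast.

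**6. Timing.** The calculation treats exposure as present at every sample. Samples fall at 1, 2 and 4 hours and just before doses 2, 3 and 5. If the five doses are spread evenly at 24/5 = 4.8-hour intervals (an assumption), four of the six samples are taken within the first 4.8 hours. A drug started after that can affect only the last two.

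**The case against.** The strongest objection is that the confounding is conjecture. Nothing in the documents says that a listed drug will be given perioperatively, how often, or more often to inflamed patients. They also do not compare the inhibition from a short course with that from chronic therapy. All of this stands. A reader might infer that inhibitor use is a direct confounder of Objective 3 that makes ODT look lower in inflamed patients. The documents do not support that: it needs unequal use in one particular direction, and step 3 shows that the direction comes from the assumption.

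The second objection concerns how exposure arises. The Background says that CYP2D6 polymorphism contributes to differences in tramadol's side effects. If an antiemetic on the list is given for tramadol-related nausea, exposure may follow from metabolite level or genotype. If it follows from inflammation, removing exposed patients changes the effect being estimated. Either way, leaving out exposed patients can itself select. This also stands. It argues for a sensitivity analysis beside the main one, and against repeating Objective 2 without exposed patients.

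Third, a reader might want one yes/no, time-updated covariate for all interacting drugs. The Statistical analysis plan contains no concentration model to hold it. One term would also mix the ODT and NDT pathways, and inhibitors with inducers, whose effects may cancel.

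Late-started drugs reach fewer samples (step 6), so the size may be smaller than shown. None of these objections supplies a record of exposure, which is the gap that remains.

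**Conclusion.** The point holds as a gap in recording and analysis, not as demonstrated bias. The exclusion is limited to chronic therapy although its rationale may extend to perioperative and ICU doses, and the plan could not detect such exposure afterwards. If use differs by inflammation status, the Objective 3 contrast could be distorted in either direction. Under the assumed exposures (20–40% v 10%) and ODT reduction (20–60%), ODT is 2–19% lower in the more exposed group, unchanged with equal use, and about 2–24% higher in inflamed patients if the shares are reversed. The rejection rates rest further on an assumed CV of 0.5 and 50 patients per group.

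The issue for NDT is narrower. The plan attributes NDT formation to CYP2B6 and CYP3A4 but does not address drugs acting on them. No size was calculated for this.

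The change is worth making because it is cheap and decides whether an ODT difference can be attributed to inflammation at all.

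**What to change.** Keep the chronic-use exclusion and add:

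> Any listed CYP2D6 inhibitor given from the day before surgery to the last plasma sample will be recorded with drug and time from the drug chart. Its use will be reported by inflammation group, and the Objective 3 comparisons of tramadol, ODT and NDT will be repeated, as a labelled sensitivity analysis, without patients (or samples) exposed before sampling.

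State in advance whether patients or samples are dropped. Dropping patients keeps the six-sample series complete for the repeated-measures and Friedman tests. Dropping samples keeps more data for comparisons at single time points.

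Record drugs acting on CYP2B6 or CYP3A4 separately, against a named list and for NDT only. Do not pool them with the CYP2D6 inhibitors, or inhibitors with inducers. The end of the exclusion list is garbled in the available text, so the sponsor should confirm the full list before it is used as the reference.

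The cost is one case-report-form item for the listed inhibitors, a separate record for the CYP2B6/CYP3A4 drugs, and a repeat of tests already planned. No treatment is restricted. The downsides are some loss of precision in the sensitivity analysis and possible selection if exposure follows from inflammation or metabolite level. For that reason it should not replace the main analysis.

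### CYP2D6 inhibitors are excluded only as long-term therapy, so a listed drug first given between induction and the last sample goes unrecorded and may bias the ODT comparisons by an unknown amount

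*Combined protocol and SAP*

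**What the plan says.** Patients and methods excludes patients "as well as those on chronic therapy with cimetidine, paroxetine, pimozide, metoclopramide, amiodarone, olanzapine", and the list continues with "chlorpromazine, fluphenazine, haloperidol, thioridazine" and others. (The end of the list is garbled in the available text, which does not affect this point.) The stated reason is that these "drugs inhibit the activity of CYP2D6 enzyme important in tramadol metabolism". The Background gives the pathway: "O-demethylation of tramadol to the active metabolite O-demethyltramadol (ODT) is catalyzed by cytochrome CYP2D6".

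Genotyping then narrows the analysis set: "ultrafast and slow metabolizers will be excluded from further analysis". This leaves extensive (EM) and intermediate (IM) metabolizers, classified by genotype alone.

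Sampling is at 1, 2 and 4 hours after the first tramadol dose and just before doses 2, 3 and 5: "In total, therefore, there will be 6 measurements within 24 hours". During this period the only co-medication that the plan says will be recorded is the additional analgesic. On side effects it says: "Nausea, vomiting, and newly developed respiratory depression will be reported within 24 hours". It does not mention what is given for them.

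Objective 2 is to "examine differences in tramadol, ODT and NDT concentrations with respect to CYP2D6 gene polymorphism". Objective 3 asks the corresponding question for systemic inflammation. The Statistical analysis plan offers two-group and multi-group tests, correlations, and a repeated-measures ANOVA or Friedman test across the six measurements. It has no covariate, stratification or sensitivity analysis for co-medication.

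**The concern.** The reason for the exclusion has no time element, but the rule does. A listed drug started at induction or in the ICU is not long-term therapy, so the patient remains eligible. The same paragraph sets a dated window for prior tramadol (7 days), yet sets none for inhibitors. Because ultrarapid and poor metabolizers are removed by genotype only, a patient whose CYP2D6 is inhibited by a drug keeps the EM or IM label.

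The plan's own Background makes such exposure hard to tell apart from the effect under study. It says that when O-demethylation falls, tramadol is mainly N-demethylated, and that higher IL-6 went with N-demethylation. Lower ODT with a shift towards NDT would therefore be expected from an inhibitor, and it is also the pattern that Objective 3 would attribute to inflammation. Exposure could also follow the grouping variable. For example, a pulse above 90/min counts towards the systemic inflammatory response, and a listed drug might be given to patients with a fast heart rhythm. That link is a possibility, not something the documents state.

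At stake are the ODT contrasts in Objectives 2 and 3. Without a record of exposure, nobody could tell afterwards whether they were affected.

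**Working it through.** The plan gives no sample size, effect size, SD, rate of inhibitor use or strength of inhibition, so there is no figure of its own to reproduce. The check has two parts.

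**1. Does any other part of the plan close the gap?**

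- Exclusion criteria: long-term use only.
- Genotyping: removes patients by genotype, not by actual enzyme activity.
- ICU care and sampling: no rule on listed drugs.
- Pain and side effects: the additional analgesic is recorded; other drugs are not mentioned.
- Statistical analysis plan: unadjusted comparisons only.

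Nothing closes it.

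**2. How large could the effect be?** All inputs below are assumptions.

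*Objective 3.* Let p1 and p0 be the exposed shares among inflamed and non-inflamed patients, and r the fractional fall in ODT at an affected sample. With no true inflammation effect, the ratio of mean ODT is

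(1 − p1·r) / (1 − p0·r).

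Take p1 = 20-40%, p0 = 10-20% and r = 30-70%. The ratio falls as p1 rises, rises as p0 rises, and falls with r whenever p1 exceeds p0. The extremes therefore lie at the corners of these ranges:

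| p1 vs p0 | r = 30% | r = 50% | r = 70% |
|---|---|---|---|
| 20% vs 20% | 0.94/0.94 = 1.00 | 0.90/0.90 = 1.00 | 0.86/0.86 = 1.00 |
| 20% vs 10% | 0.94/0.97 = 0.97 | 0.90/0.95 = 0.95 | 0.86/0.93 = 0.92 |
| 40% vs 20% | 0.88/0.94 = 0.94 | 0.80/0.90 = 0.89 | 0.72/0.86 = 0.84 |
| 40% vs 10% | 0.88/0.97 = 0.91 | 0.80/0.95 = 0.84 | 0.72/0.93 = 0.77 |

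The range is 1.00 to 0.77, that is, from no bias to a spurious 23% reduction.

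*Timing.* These ratios apply to a sample taken under inhibition. A drug started after the 4-hour sample and before dose 2 leaves three of the six samples untouched. With the six samples weighted equally, the average fall is r/2. The worst corner then becomes (1 − 0.40 × 0.35)/(1 − 0.10 × 0.35) = 0.86/0.965 = 0.89 instead of 0.77.

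*Objective 2.* If a share f is exposed in both genotype groups and ODT falls by a fraction h, the EM-IM difference is multiplied by (1 − f·h). At constant SD, the sample size needed is multiplied by about 1/(1 − f·h)²:

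- f = 10%, h = 25%: 0.975 of the difference remains; sample size × 1.05
- f = 30%, h = 50%: 0.85 remains; × 1.38
- f = 50%, h = 75%: 0.625 remains; × 2.56

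This holds for equal exposure. If exposure differs by genotype, the direction depends on which group is exposed more.

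**The case against.** The strongest objection is that the risk is conditional at every step. The documents do not say that any listed drug is given in this ICU during the 24 hours. They say that nausea and vomiting will be reported, not that they are expected or how they are treated. They say that the listed drugs inhibit CYP2D6, but not that a first dose does so within hours, or as strongly as established therapy. This stands. A reader might infer that the ODT contrasts will be distorted, or that samples after a first dose are under the same inhibition as in a long-term user. The text supports neither.

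A reader might also infer that some bias is always present. It is not: equal exposure in the two inflammation groups gives a ratio of exactly 1.00. Nor do the documents show that nausea follows high ODT, so the argument that nausea-driven treatment would selectively lower ODT in EM patients has no support in them.

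Finally, the obvious remedy of dropping post-exposure samples from the main analysis has its own bias. If exposure follows inflammation or ODT level, late samples would be lost selectively. Repeated-measures ANOVA and the Friedman test in standard form need complete series, so the whole patient could drop out. A time-varying covariate would need a model that the plan does not contain. This also stands, and it determines the fix.

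None of this closes the gap. Under the plan as written, exposed patients remain in the comparisons and cannot be identified.

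**Conclusion.** The gap is real: inhibitors are excluded only as long-term therapy, first use between induction and the pre-dose-5 sample is not recorded, and the analysis does not account for it. The consequence is a possible bias of unknown size. Under the stated assumptions, the spurious inflamed/non-inflamed ODT ratio in Objective 3 lies between 1.00 and 0.77 at affected samples, and nearer 1 when averaged with samples taken before exposure. In Objective 2, equal exposure of 10-50% with ODT lowered by 25-75% would leave 97.5% down to 62.5% of the EM-IM difference. If use of listed drugs is rare, or brief exposure inhibits only weakly, the effect is small. The documents do not settle which case applies, and without a record the study could not settle it either. The point deserves correction because the remedy is cheap. It does not show that the planned comparisons are invalid.

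**What to change.** - In Patients and methods, add that the drug and time of each listed CYP2D6 inhibitor given from induction to the pre-dose-5 sample will be taken from the ICU drug chart and, for the operation itself, the anaesthesia record.
- Report the number and share exposed by inflammation group and by genotype group.
- In the Statistical analysis plan, keep all samples in the main analysis. Pre-specify a sensitivity analysis for Objectives 2 and 3 that leaves out exposed patients or, where time points are compared one by one, their post-exposure samples.
- State that this sensitivity analysis is itself selective if exposure follows illness severity, so it tests robustness and does not replace the main result.

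The cost is one extra field on the case record, one extra analysis and a smaller sample in that analysis. If exposure proves rare, the record will show it. This concerns data capture and analysis only; no change to patient care is proposed.
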